RESEARCH PROTOCOL

Pragmatic randomised controlled trial of an intervention to reduce burnout and improve well-being in NHS doctors

Short title of study

CPM Trial 2

Protocol version and date	Research Ethics Committee (REC) reference
(v8) 19/04/2024	23/SW/0075
Sponsor organisation	Controlled trials registration number
Rotherham Doncaster and South Humber NHS Foundation Trust	ISRCTN14947225

Research team

[name]^{1,2}, [name]², [name]^{1,2}, [name]², [name]³, [name]⁴, [name]², [name]²

- 1 Clinical Psychology Unit, Department of Psychology, University of Sheffield, UK
- 2 Rotherham Doncaster and South Humber NHS Foundation Trust, UK
- 3 Sheffield Teaching Hospitals NHS Foundation Trust, UK
- 4 Academic Unit of Primary Medical Care, University of Sheffield, UK

Chief investigator contacts details

[name]

[name] Email: [contact]

Contents of the study protocol		Pg.
1.	Synopsis	2
2.	Background and rationale	3
3.	Objectives and research questions	3
4.	Study design	4
4.1	Setting and participants	5
4.2	Intervention	6
4.3	Measures and a substitution of the substitutio	
4.4	Recruitment, study procedures and data collection	
5.	Data analysis	6
6.	Ethical considerations	7
7.	Dissemination plan	
8.	References	8

1. Synopsis of the study		
Short study title	CPM Trial 2	
ISRCTN registration no.	TBC	
Study Design	Pragmatic, stepped-wedge randomised controlled trial	
Setting	Hospital and community-based NHS providers	
Study Participants	GMC registered doctors working in the National Health Service	
Primary Objective	To evaluate if a group-based psychological intervention reduces occupational burnout levels in doctors	
Secondary Objectives	 To assess if the intervention improves subjective well-being To quantify completion and dropout rates To investigate predictors of dropout and treatment response To examine variability in burnout, well-being and job satisfaction according to role and demographic characteristics To understand participants' experiences of the intervention 	
Primary outcome	Occupational burnout, measured by the Oldenburg Burnout Inventory (OLBI)	
Intervention	An 8-session, 10-week, group-based, psychoeducational intervention based on The Mind Management Skills for Life Programme	
Randomization and data collection	Consenting NHS doctors will be randomly assigned to two groups; 1 and 2. Participants in both groups will be asked to complete outcome measures at an initial baseline assessment, after which only participants in group 1 will access an 8-session, 10-week intervention (controlled phase). Next, group 2 will access the intervention during an 8-session, 10-week period (full implementation phase). Finally, we will collect further outcome measures 6 months after both groups have completed the intervention (follow-up phase). Following intention-to-treat principles, participants who do not attend any intervention sessions (and who do not formally withdraw) will be included in the study and will be invited to complete measures.	
Planned Sample Size	Minimum recruitment target of 180 participants, expecting 50% attrition, plus approx. 120 non-intervention participants.	
Data analysis method	 Trial data will be summarised using a CONSORT diagram and analyses will be based on intention-to-treat principles. The primary analysis will compare between-group differences in OLBI at 10-weeks, using ANCOVA adjusting for baseline OLBI. Secondary analyses: Between-group comparisons will be conducted at each measurement point using ANCOVA adjusting for baseline severity in the relevant outcome measure. Between-group and within-group effect sizes will be calculated using Cohen's d. Completion / dropout rates will be compared between groups using chisquare analysis. Predictors of dropout and treatment response will be examined as a secondary analysis using Elastic Net regularization Variability in burnout, wellbeing and job satisfaction will be examined across groups defined by job role and demographic characteristics using t-tests and appropriate non-parametric tests. Qualitative data will be analysed using thematic analysis. 	
Study Period	24 months (18 months active study period, plus 6 months analyses and dissemination)	

2. Background and rationale

Occupational burnout refers to a state of job-related emotional exhaustion, depersonalisation and reduced personal accomplishment (Maslach, 1982). Burnout is known to be particularly severe in healthcare professionals such as doctors. A 2020 survey by Medscape UK found that the number of doctors experiencing depression and burnout has increased by 68% since 2018, and that many doctors now say they are considering changing careers or retiring early. A systematic review by Williams et al., (2020) found that burnout can have a significant impact on the physical and mental health of doctors. For example, in the 16 studies that examined the link between burnout and depression, they found that burnout was significantly related to depression in six studies. In the seven studies that explored burnout and its link with physical health outcomes three studies supported a relationship between increased burnout and worse physical health outcomes. It is also worthy of note that of five studies looking at the link between burnout and suicidal thoughts, three studies found support for this relationship. For all of these findings, emotional exhaustion seemed to the component of burnout that was most often related to these negative consequences.

A study by Hall et al., (2020) found that burned out doctors felt they were likely to have decreased empathy and listening skills. Doctors were also more likely to report negative attitudes towards patients, leading to fewer good quality interactions. Finally, doctors reported that they were likely to complete inappropriate referrals, potentially leading to unnecessary investigation and increased emotional distress for patients. Hall et al., (2020) further noted impact on patient safety. They felt issues like a lack of space to think, and inability to approach the patient holistically were likely to cause indirect negative effects on patient safety. Poorer concentration and increased tiredness could also potentially lead to poor decision making. Finally, Hall et al., (2020) note that burnout and mistakes are likely to work in a downward spiral. The more burnt out a doctor is, the more likely they are to make mistakes or have complaints made about them, but also making mistakes or receiving complaints is likely to increase burnout (Hall, et al., 2020). Other studies (not focussed on doctors) show the link between burnout and poorer patient treatment outcomes (Delgadillo, Saxon, & Barkham, 2018), medical errors (Shanafelt et al., 2010), medico-legal cases (Balch et al., 2011), and healthcare related infections (Cimiotti et al., 2012). Burnout can also lead to increased absenteeism and staff turnover (Lee, Lim, Yang, & Lee, 2011; Salvagioni et al., 2017).

A recent examination of staff well-being in the English National Health Service (NHS) concluded that staff shortages related to occupational stress are linked with poor quality of care and poor patient experience (Sizmur & Raleigh, 2018), highlighting the widespread nature of burnout and its impact in the NHS. Burnout in the NHS is a system wide problem with Public Health England estimating the cost of staff absence due to poor health at £2.4 billion per annum. The NHS depends on having a healthy and productive workforce to deliver high quality patient care. The Boorman NHS Health and Well-being 2009 report found that 80% of staff felt that their health and wellbeing had an impact on patient care, but only 40% of staff felt their employer was proactively trying to improve their health and wellbeing. A recent survey of doctors found that around 97% of respondents felt that the NHS has a culture of seeing excessive stress and workload as the norm (Dominic, Gopal & Sidhu, 2021). The gravity of these issues has led to calls for the NHS to make the health and wellbeing of its staff a priority. Their 2015 report 'Work and wellbeing in the NHS: Why staff health matters to patient care' recognises the importance of staff health and wellbeing to both NHS organisations and patients and concludes that our healthcare system's greatest asset is the people who deliver it. As NHS services face unprecedented clinical demand, increasing financial pressures and a patient population with complex care needs, it is often the health and wellbeing of NHS staff that suffers.

Factor in the Covid-19 pandemic, and the outlook is even bleaker. Working during the pandemic has had a great impact on the wellbeing of doctors, resulting in an increase in burnout. Prior to the pandemic in 2020, 32% of doctors reported an impact on their wellbeing, in comparison to 42% of doctors who worked throughout covid (GMC,2021). The doctor's field of work is also something that has an impact on their risk of burnout (GMC,2021). Those with the highest risk of burnout were G.P.s (32%), followed by specialists (18%), doctors in training (11%) and finally SAS and LE doctors (7%).

For these reasons, and given the scale of the problem, the NHS Long Term Plan acknowledges the need to "support improved health and wellbeing of staff and management of sickness absence" (NHS England, 2019, pg. 87).

Approaches to address occupational burnout include individual interventions (e.g., stress management courses, mindfulness courses, cognitive-behavioural coping skills training, communication training) and structural / organisational interventions (e.g., workload redesign, practice delivery changes). Numerous studies have measured the positive effect of such interventions (Lucas et al., 2012, Linzer et al., 2015), although relatively few controlled trials have been conducted with healthcare professionals. A meta-analysis of controlled trials and cohort studies concluded that both individual-focused and organisational strategies can reduce burnout in healthcare professionals by approximately 10% (West, Dyrbye, Erwin, & Shanafelt, 2016). Overall, there is some evidence that both individual and organisational interventions can help to ease occupational burnout, and coping-skills interventions appear to be promising in healthcare staff. Despite this emerging literature, evidence-based interventions to prevent or reduce burnout are not routinely offered to NHS staff. In particular, there is limited research on the efficacy of burnout-focused interventions in doctors working in publicly funded healthcare organisations such as the NHS, who are known to experience particularly high levels of burnout by comparison to other health professionals. Although observational studies indicate that doctors could potentially benefit from burnoutinterventions, there are only a few rigorous clinical trials of such interventions, and most are small and underpowered to draw firm conclusions. The present study aims to address this gap in the literature by conducting an adequately powered multi-site randomised controlled trial to test the efficacy of a digitallyenabled intervention for occupational burnout in NHS doctors.

3. Objectives and Hypotheses

3.1. Primary Objective

To evaluate if a group-based psychological intervention reduces occupational burnout levels in NHS doctors.

3.2. Secondary Objectives

- To assess if the intervention improves subjective well-being
- To assess if the intervention improves job satisfaction
- To quantify completion and dropout rates
- To explore predictors of dropout and treatment response
- To examine variability in burnout and well-being according to role and demographic characteristics
- To understand participants' experiences of the intervention

3.3. Hypotheses

[figure not shown]
- A) Exposure to the intervention will be associated with significantly lower mean burnout severity by comparison to a waitlist (delayed intervention) control group
- B) After the control group is exposed to the intervention, there will be no significant differences in mean burnout level between the two groups (immediate intervention group, delayed intervention group)
- C) Mean burnout severity for all participants at the end of the 6-month follow-up period will be significantly lower than baseline severity (prior to intervention), but not significantly different to endof-treatment severity, indicating maintenance of gains

4. Study design

This will be a pragmatic, stepped wedge, open-label, randomised controlled trial. Consenting doctors will be randomly assigned to two groups, by a research assistant using a computerized randomization algorithm. The randomisation sequence will be based on random blocks of 10 participants, and

stratification according to participants' employing organisation (trial site). The study will be carried out in three phases, which are illustrated in Figure 1.

Figure 1. Stepped wedge trial design

Participants in both groups will be asked to complete outcome measures during a pre-intervention baseline assessment (week 0). After the baseline assessment, only participants in group 1 will access an 8 session, 10-week intervention (controlled phase). Next, group 2 will access the intervention during a 10-week period (full implementation phase). Finally, we will collect further outcome measures 6 months after both groups have completed the intervention (follow-up phase). Selected outcome measures (see section '4.3 Measures' for more details) will be completed at each of the measurement points outlined in the above timeline (weeks 0, 10, 20, 44). All measures will be completed online using an industry-standard survey system (Qualtrics), which will be managed by a research assistant.

The end of the study is classed as once the participant has completed the six-month follow-up questionnaire. However, the participants email addresses will be kept for up to six months after this to ensure the research team can disseminate the results of the study. Following this, all personal data will be deleted.

Participants who do not attend at least one intervention session will be classed as part of a 'non-intervention' group. The baseline data for these participants will be retained and, unless they have formally withdrawn, they will be invited to complete the questionnaires at each of the above timepoints so we can include their outcome measures in the primary data analysis, following intention-to-treat principles (see section 5.2).

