5.1. Sample size calculation

Using G*Power to perform a sample size calculation for a between-groups analysis of covariance (ANCOVA), with 80% power, an alpha level of 0.05, and controlling for intake severity to detect an effect size of d=0.6 (based on the CPM 1 trial (ISRCTN34503872) - converts to f=0.30) estimates that at least 45 participants are needed in each group (total sample size of 90).

Accounting for a drop-out rate of 50% (based on the lost-to-follow-up rate at 6-month follow-up in CPM 1), would inflate the total required sample size to a minimum of 180 (90 in each group). This high dropout rate is associated with the busy nature of healthcare, which makes it difficult to retain NHS staff in clinical trials, and hence it is essential to work to a conservative sample size calculation.

For reference, CPM 1 recruited a total of 173 participants (G1=83, G2=90). So, if we were to account for the expected follow-up drop-out rate, we would need to recruit more participants than CPM 1. Therefore, to ensure that the trial is adequately powered and robust to the expected level of attrition, we propose to recruit a minimum of 180 participants and to continue to recruit as many participants as are willing to provide consent within the 3-month recruitment period. In order to ensure the trial recruits to target and is robust to attrition, we will recruit from multiple NHS service providers across England.

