5.3. Secondary analyses

The analysis described above will be repeated at the 44-week follow-up. In addition, these analyses will be repeated at each of the post-intervention time-points illustrated in Figure 1 (weeks 10, 44), using the OLBI sub-domain scores (*exhaustion*; *disengagement*), the WEMWBS well-being measure, and the JDSS job satisfaction measure, controlling for baseline scores. These between-group comparisons will also be summarised using effect sizes (Cohen's d).

Post-intervention measures (weeks 10, 20, 44) will be compared to baseline measures (week 0) within each group, using paired-samples t-tests or an appropriate non-parametric test depending on the distribution of the data. Within-sample pre-post treatment effect sizes will also be computed using the method proposed by Minami et al. (2008).

Dropout will be defined as attending less than 4 (half) of the intervention sessions. We will examine predictors of dropout and treatment response (defined as reliable improvement in the OLBI measure), using all available baseline measures as candidate predictors. Reliable predictors of each of these outcomes of interest will be identified using a variable selection method called Elastic Net Regularization (Zou & Hastie, 2005) applied in separate logistic regression models for each dependent variable.

Additional secondary analyses will examine variability in burnout, wellbeing and job satisfaction across groups defined by their job role and demographic characteristics. Between-group comparisons will be made using t-tests (or Mann-Whitney U Tests if the data are not normally distributed).

Qualitative data collected via online surveys after all participants had the opportunity to access the intervention (week 20) will be analysed using thematic analysis (TA). TA will follow the 6-step phase of

analysis proposed by Braun and Clarke (2006). We will triangulate qualitative themes generated via the TA method with baseline survey data in order to explore if the themes vary according to job role (e.g., junior doctors, consultants, etc.) and setting (e.g., community vs. hospital services).

6. Ethical considerations

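### Hypothesis B and the maintenance half of Hypothesis C count a non-significant test as confirmation, with no margin, and section 5.3 lists no week-44 versus end-of-treatment comparison

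*Protocol*

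**What the plan says.** Hypothesis B (Protocol 3.3) reads: "After the control group is exposed to the intervention, there will be no significant differences in mean burnout level between the two groups". Hypothesis C, for all participants, has two halves. Week-44 burnout is to be significantly lower than baseline, "but not significantly different to endof-treatment severity, indicating maintenance of gains". No equivalence or non-inferiority margin appears in the protocol.

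The sample size (5.1) is for a superiority ANCOVA "with 80% power, an alpha level of 0.05, and controlling for intake severity to detect an effect size of d=0.6", giving "at least 45 participants are needed in each group (total sample size of 90"). The 50% inflation to 180 is introduced with "Accounting for a drop-out rate of 50% (based on the lost-to-follow-up rate at 6-month follow-up in CPM 1"). The 180 is a minimum, and recruitment continues above it for the rest of the recruitment period.

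Section 5.3 repeats the primary OLBI ANCOVA at week 44. For the OLBI sub-domains, well-being and job satisfaction, "these analyses will be repeated at each of the post-intervention time-points illustrated in Figure 1 (weeks 10, 44"). Within each group it compares weeks 10, 20 and 44 with week 0. The synopsis is wider: "Between-group comparisons will be conducted at each measurement point using ANCOVA adjusting for baseline severity". Section 5.2 imputes missing data by expectation-maximization before analysis.

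**The concern.** A hypothesis worded as a non-significant result is met whenever the test fails to reject, whether because the groups are alike or because the data are too imprecise to tell. Hypothesis C goes further and names the inference: non-significance is read as maintained gains. The trial has 80% power for 0.6 SD and much less for the smaller differences that would matter to a claim of equal benefit or durability. Two of the three stated hypotheses could therefore be reported as supported through imprecision. In addition, the maintenance clause needs a comparison that section 5.3 does not list.

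**Working it through.** **Inputs.** From 5.1: alpha 0.05, d=0.6, 90 evaluable, 50% loss. Baseline and between-visit correlations (r) are not in the protocol; 0.5 to 0.7 is an assumed range, and r=0 is the unadjusted case. Differences are in SD units of the OLBI.

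**The plan's own figure.** f = d/2 = 0.30 ("converts to f=0.30"). With two groups and one covariate, noncentrality = f² × N = 0.09 × 90 = 8.1 on 1 and 87 df, giving power 0.804; 90 is the smallest N reaching 0.80. Then 90/(1 − 0.5) = 180. Both figures reproduce.

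**Hypothesis B, true difference 0.3 SD (half the design effect).** f² = (0.3/2)²/(1 − r²), noncentrality = f² × N, and half-width = t × 2√(1 − r²)/√N.

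| Baseline r | Noncentrality, N=90 | P(non-significant), N=90 | 95% CI half-width, N=90 | P(non-significant), all 180 observed |
|---|---|---|---|---|
| 0 | 0.0225 × 90 = 2.03 | 71% | 0.42 SD | 48% |
| 0.5 | 0.0300 × 90 = 2.70 | 63% | 0.36 SD | 36% |
| 0.7 | 0.0441 × 90 = 3.97 | 50% | 0.30 SD | 20% |

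**Hypothesis C, true relapse 0.2 SD (paired t-test).** Noncentrality = 0.2√n/√(2(1 − r)).

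| Pairs | r=0.5 | r=0.7 |
|---|---|---|
| 90 (pooled) | 1.90, missed 53% | 2.45, missed 32% |
| 45 (one group) | 1.34, missed 74% | 1.73, missed 60% |

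**Effect of imputation on B.** The figures above are for observed data, whereas the planned ANCOVA uses imputed data. I simulated 90 per group with half the outcomes missing at random, single conditional-mean imputation, assumed r=0.6 and a true difference of 0.3 SD. With group in the imputation model, the result is non-significant about 21% of the time, but about 34% of trials with no true difference come out significant. With group left out, it is non-significant about 59% of the time. For reference, observed cases alone give 57% at r=0.6. Complete data on 180 give about 29% (noncentrality 0.0225/0.64 × 180 = 6.33). Imputation can thus land on either side of the complete-data rate. The protocol does not say which imputation model applies.

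**Could a margin be met?**
- For B, with true difference zero, 80% power and a 95% CI inside ±0.3 SD, n per group = 2(1 − r²)(1.960 + 1.282)²/0.3² = 234 at r=0 and 120 at r=0.7. With 45 per group the power is 0% at r=0 or 0.5 and about 3% at r=0.7. A 90% CI raises the r=0.7 figure only to 27%.
- For maintenance as paired non-inferiority (one-sided 0.025, 80% power), pairs = 2(1 − r)(1.960 + 0.842)²/margin². A 0.3 SD margin needs 88 (r=0.5) or 53 (r=0.7); a 0.2 SD margin needs 197 or 118. About 90 are expected.

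**Hypotheses against listed analyses.**

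| Needed | Section 5.3 | Synopsis |
|---|---|---|
| B: groups at week 20 | not listed | covered by its general wording |
| B: groups at week 44 | listed for OLBI total | covered |
| C: week 44 vs week 0 | listed, within each group only | not itemised |
| C: week 44 vs end of treatment | not listed | not itemised |

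End of treatment is week 10 for Group 1 and week 20 for Group 2, so the missing comparison spans 44 − 10 = 34 weeks in one group and 44 − 20 = 24 in the other. A pooled version must be defined.

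**The case against.** The strongest reply is that B and C touch neither the primary week-10 test nor the sample size, that neither equality nor maintenance is a listed objective, and that margins and exact contrasts are often left to an SAP. Adjusted 95% confidence intervals and Cohen's d are already planned for the between-group ANCOVAs. All of this limits the severity. It does not remove the point, because section 3.3 itself fixes the inference rule.

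Four stronger readings are tempting and are not supported:
- A reader might infer that 5.3 offers no test of B. It does: the OLBI ANCOVA at week 44 falls after both groups have been treated. The sentence limited to weeks 10 and 44 concerns the other scales. For B the gap is week 20 and a disagreement with the synopsis.
- A reader might infer that durability would be declared whenever the data are imprecise. C also requires a significant fall from baseline, which imprecision works against.
- A reader might infer that losing data always makes confirmation easier. For B that depends on the imputation model. In addition, 180 is a minimum, and the 50% is a 6-month rate that may overstate loss at week 20.
- A reader might infer that the week-44 ANCOVA is presented as a treatment effect. The protocol does not say so, and B labels the arms as immediate and delayed intervention.

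**Conclusion.** The point stands for Hypothesis B and the maintenance half of C; the other half of C is unaffected. With about 45 observed per group, a true 0.3 SD group difference would pass as no difference about 71% of the time unadjusted, or 63% to 50% at assumed correlations of 0.5 to 0.7. A true 0.2 SD relapse would pass as maintenance on that test 53% to 32% of the time with 90 pairs. These rates assume observed-case analysis and correlations that the protocol does not give. Single imputation can change the rate for B substantially but does not make non-significance valid evidence of equality. The week-44 versus end-of-treatment comparison is absent from 5.3, and 5.3 and the synopsis disagree on week 20. This should be corrected; it does not threaten the primary conclusion.

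**What to change.** In 3.3, delete the clauses that predict a non-significant result. State B and the maintenance part of C as estimates with 95% confidence intervals, concluding similarity or maintenance only if the interval excludes a margin fixed before analysis. The margin must be justified on the OLBI scale. State openly that a 0.3 SD equivalence margin for B is not reachable at 45 per group, so B is likely to remain an estimate only.

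In 5.3, add the change from each group's own end of treatment (week 10 for Group 1, week 20 for Group 2) to week 44, and say how the groups are combined for the all-participants statement. Add the week-20 between-group OLBI ANCOVA so that 5.3 agrees with the synopsis.

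The cost is wording in the protocol and SAP, with no new data. The downside is that the trial may be unable to claim equality or maintenance.
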